5. STUDY DESIGN

The research design is a mixed method pilot study with nested longitudinal qualitative interviews and questionnaires.

The value of undertaking a pilot study is to gain an understanding of interventional suitability without costly and time intensive research activity and probable risk of study failure (Bell et al. 2018) In addition to providing useful information concerning the protocol design and implementation (Hassan et al. 2006).

The mixed method approach used in this study consists of semi structured interviews with participants and deliverers (Equality Health Advisors), including validated questionnaires at baseline and at a 12-week time point.

This is a single centre study recruiting participants registered within the Aneurin Bevan University catchment area in a secondary care setting.

The pilot study identification, screening, and consent will take place in the following Aneurin Bevan University Health Board hospital sites.

- Grange University Hospital (GUH)
- Royal Gwent Hospital (RGH)
- Nevil Hall Hospital
- Ysbyty Ystrad Fawr (YYF)
- Cwmbran PAD Clinic

Identification and screening will be discerned by the participants care team; this includes first contact. Consent will be conducted by the research delivery team, and may include care team, research nurse, CI, or PI.

This is a place-based intervention - Ideally all contact visits within the intervention will be undertaken in the participant's home. However, participants will be offered an alternative option of a video link if this is not applicable.

6. STUDY MANAGEMENT

Study Project Team (SPT) - Weekly Meetings

This team will include CI, PI, co-investigator, members of the participants care team, research nurse and Equality Health Advisors. This team will discuss recruitment, CRFA, participant comments/ participant home visits, protocol queries, participant queries, data queries, CRFB participants comments/ potential study risks/ escalations.

Study Management Group (SMG) - Monthly Meeting

Study management will consist of a monthly supervisory meeting with the researcher and two Cardiff University supervisors. Including, ABUHB Quality Assurance Officer Independent Data Validation Reviewer (Quantitative) Independent Data Validation Reviewer (Qualitative)

Study Operational Group (SOG)

[figure not shown]
There will be a quarterly SOG meeting which will include health professionals, researchers and patient and public persons during the implementation phase to help inform amendments to the protocol if necessary. This group will receive regular reports from the researcher with details of progress including summary of screening logs, numbers recruited and completed outcome assessments, and study protocol deviations.

Patient and Public Involvement (PPI) Advisory Group

As part of the study two PPI members with lived experience will join the SOG.

7. STUDY FLOW CHART and/or SCHEDULE OF STUDY PROCEDURES

Diagram 1: Equality Health -CVD - Intervention developed by the researcher in conjunction with Professional and PPI consultation

Procedures	Weeks				
Intervention	Screening				
	O weeks	Week1	Week 4	Week 8	12 weeks
Eligibility criteria review	х				
Informed consent	х				
Medical history	х				

Case Report Form A	X				
Including audit c	^				
Health Check		х			Х
(Including Weight, HR, BP, BMI, Waist Circumference)					
EQ-5D	х				Х
PROMIS 10	Х				Х
South Wales Social Wellbeing Scale	х				х
Equality Health Home Visit form		х	х	х	X
Case Report Form B					х
Including audit c					
Semi Structured Interview					x

8. PARTICIPANT IDENTIFICATION

8.1. Study Participants

The sample size is 20 participants. In this instance, time and resource constraints make recruiting a larger sample challenging. While 20 participants may be smaller than the typical guideline of 30 suggested by (Billingham et al. 2013) it may still provide valuable insights.

8.2 Inclusion Criteria

To obtain person centred standards a series of professional and public, patient engagement sessions were arranged to develop and finalise the EQUALITY HEALTH-CVD protocol. Dedicated discussion groups' and 'one-to-one consultation meetings' with professionals and those with lived experience helped address any challenges and improved the quality of the protocol research design. The recommendations included narrowing the eligibility criteria to focus only on participants diagnosed with transient ischaemic attack, peripheral vascular disease and ischemic stroke NIHSS score of 5 and below. This will ensure that clinical input

after hospital discharge does not compound intervention results and reduces the burden of excessive healthcare support systems overwhelming the participants.

Patients -

- 1. (Identified as) Male and Female
- 2. ≥18–100 years of age
- History of ischemic stroke NHISS score of less than 5 And/or
- 4. History of Transient ischaemic attack And/or
- 5. Referral to Peripheral Vascular Clinic.
- 6. Capacity to consent
- 7. Willingness to partake in a qualitative interview at the end of the intervention

Equality Health Advisors for semi-structured interviews:

Undertaken the role of an Equality Health Advisor

8.3. Exclusion Criteria

Patients

- 1. Less than 18 years of age
- 2. Patients receiving or eligible for Palliative Care.
- 3. Unwillingness or inability (e.g. physical or cognitive) to comply with study procedures.
- 4. Any person already participating in a clinical rehabilitation home intervention.
- 5. Unwillingness to take part in a qualitative interview at the end of the intervention

Equality Health Advisors for semi-structured interviews:

No exclusion criteria required

9. STUDY PROCEDURES

Schedule of assessments (0 month)

Participants in the study will undergo eligibility screening in three different settings. During emergency admission in GUH, as an inpatient at YYF or during a routine clinic at various sites. The participants care team will provide potential participants with a patient information sheet.

Baseline data

All participants will be consented by a delegated member of the ABUHB research delivery team. After consent the following questionnaires will be completed

- CASE REPORT FORM A
- PROMIS 10
- EQ-5D
- South Wales Social Wellbeing Scale

The questionnaires will be collected either by Microsoft forms if Wi-Fi is available or paper form and then transferred to an excel database.

The initial consultation of the intervention date and time be organised either during baseline data collection by the ABUHB research delivery team, or via telephone or email by the Equality Health Advisor.

(Follow Up 1) Equality Health- CVD Intervention (week 1) Initial Consultation

Consented Participants will be offered an initial face to face home based appointment where the Equality Health Advisor will provide place-based support focusing on four domains.

- 1. Physiological impacts
- Health behaviours
- 3. Psycho-social factors
- 4. Wider determinants of health
- **1.**The Equality Health Advisor will conduct the following physical tests:
- Blood Pressure and HR
- Height
- Weight
- BMI
- Waist Circumference

All physical test results will be recorded - if blood pressure is considered high: Hypertension: Systolic 140 mm Hg or higher or diastolic 90 mm Hg or higher the Equality Health Advisor will advise the participant to keep track of their blood pressure at home using an automated blood pressure monitor once a day at a different time of the day for a period of seven days. If blood pressure remains high after this time the participant will be advised to seek medical support at their registered GP surgery. If the participant does not own a blood pressure monitor, a monitor recommended by the British and Irish Hypertension Society blood pressure will be provided to the participant by the study team.

If a blood pressure reading is in the category of hypertensive crisis (180/100) the Equality Health Advisor will advise the participant to seek immediate medical support.

- **2.** The Equality Health Advisor will complete an equality health home visit data collection form with the assistance of the participant. The participant will undertake a coaching session that aims to elicit a goal setting conversation to create a personal goal plan. The aim is to create a person-centred plan. There will also be an opportunity for the equality Health Advisor and participant to discuss health literacy.
- **3 & 4** Based on the information provided, the Equality Health Advisor will present a range of options to overcome barriers and address needs concerning psycho-social factors and wider determinants of health which may mean linking the participant to different services within the community. The Equality Health Advisor may need to provide extra support in helping the participant navigate different services such as contacting services on the participants behalf.

The participant will receive assistance and guidance related to the Labonte Model during this meeting, including guidance on health and lifestyle. A four-week follow-up visit will be scheduled when the amount of assistance is documented. Data collection in terms of services contacted and action log for next appointment will be documented.

Follow up 2 - (4 weeks)

The Equality Health Advisor will visit the participant at home after four weeks to follow up on progression and assist in any additional needs. The plan will be adapted if any barriers are encountered. Together, the participant and the Equality Health Advisor will identify a solution. Information about delivery time, mode, application of intervention components, and retention/adherence rate will all be gathered by the Equality Health Advisor using either an electronic device or paper reporting form that will be transferred to an excel sheet.

Follow up 3 - (8 weeks)

The Equality Health Advisor will visit the participant at home after eight weeks to follow up on progression and assist in any additional needs. The plan will be adapted if any barriers are encountered. Together, the participant and the Equality Health Advisor will identify a solution. Information about delivery time, mode, application of intervention components, and retention/adherence rate will all be gathered by the Equality Health Advisor using an electronic device or paper reporting form that will be transferred to an excel sheet.

Follow up 4 - Intervention end of study visit (12 weeks)

The final review at 12 weeks will involve a physical health check and questionnaires conducted at the baseline assessment and initial consultation. There will also be a follow up goal setting conversation to ascertain if the participant requires further

support. Information about delivery time, mode, application of intervention components, and retention/adherence rate will all be gathered by the Equality Health Advisor using either an electronic device or paper reporting form that will be transferred to an excel sheet.

The questionnaires are as follows.

- CASE REPORT FORM B
- PROMIS 10
- EQ-5D
- South Wales Social Wellbeing Scale

The physical tests are as follows:

- Blood Pressure and HR
- Height
- Weight
- BMI
- Waist Circumference

NB: If the participant feels uncomfortable with Equality Health Advisor visiting their home at any point, they will be offered an alternative of a telephone or video call. This will be recorded on the Equality Health home visit form.

Process Evaluation

Participants and Equality Health Advisor semi-structured interviews

As part of the final intervention process evaluation, a small cohort of participants (approximately 8-10) using a non-probability convenience sample as described by (Suen et al. 2014) will undertake a semi structured interview during the 12 week follow up visit. The semi structured interviews will be conducted by the researcher.

A set of standard questions will be asked to ascertain the following:

- The participant's experiences and perceptions of the Equality Health-CVD Intervention.
- The participant's acceptability of the intervention and study design.
- Challenges or opportunities of future research in reducing health inequalities in the community.

In addition, approximately 2-4 Equality Health Advisors will undertake a semi structured interview to explore their views of the EQUALITY HEALTH-CVD study using a similar thematic qualitative process as the participants.

In addition, the Equality Health Advisor will keep a reflective diary.

It should be noted that further interviews may be required if new data is still presenting itself after the final interview. This study aims to achieve theoretical saturation in that sampling will continue until eligible participant pool has been exhausted or interviews are not yielding new information.

Logic Model

Context	Intervention	Mechanisms of	Intervention outcomes
		impact	
Setting: Secondary care support service.	Link participants to community-based interventions.	Accessible pathways into service-based and	Improved physical health. Improved mental health and well-being
Target population: People diagnosed with either of the following:	Link participants to CIVIC	community-based interventions	Better Health Behaviours
 History of ischemic stroke NHISS score of less than 5 	interventions that support (Closeness, Identity, Valued	Participative social functioning Knowing who to	Increased social connectedness.
 History of Transient ischemic attack 	relationships, Involvement, Cared for/accepted) – Civic duty	contact Participant is	Reduce social isolation. Improved healthcare
Peripheral Vascular Disease	Tor/accepted) – Civic duty	Listened to	utilisation outcomes (such
Number of Participants	Provide Health and Wellbeing coaching using basis CBT.	Supporting Participant	as fewer GP visits and lowe emergency admission)
Total = 20 Aim: Improve Health and Wellbeing	(Using NHS England health and wellbeing coaches framework)	motivation Flexible role	Increase Self Efficacy in managing personal health
Age: Male and Female – Age 18 to 100 Deliverers: Equality Health Advisors	Physiological testing	Trusting interpersonal relationship Person-centred approach	Reduction in risky health behaviours Improve health literacy.
Number of Visits: 4 visit in total – approximately 4 week apart	BMI Waist Circumference	Adaptability of intervention Cross pathway	Support health awareness through physiological testing.
Length of Visit: Approximately 1 hour	Act upon wider determinants of health Fuel poverty -Nest Income – Citizens Advice	referrals	Increased engagement in preventive health behaviours

	Poor housing and living	Improve disease
	conditions.	management.
	Education	
	Unemployment	Greater awareness of social
	Health care service	determinants of health
		Increase access to essential
		services (e.g., healthcare,
		transportation)
I .	I and the second	

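### About 8-10 interviewees are to be taken by convenience although every participant must already be willing to be interviewed, so a complete sampling frame goes unused and saturation may be declared before a small group is heard

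*Protocol*

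**What the plan says.** Protocol section 8.1 sets the cohort: "The sample size is 20 participants". Section 8.2 lists among the inclusion criteria "Willingness to partake in a qualitative interview at the end of the intervention", and section 8.3 lists the mirror image among the exclusions: "Unwillingness to take part in a qualitative interview at the end of the intervention". Nobody can be enrolled without having agreed to an interview.

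Section 9 (Process Evaluation) then plans interviews with about 8-10 participants, selected "using a non-probability convenience sample". These people "will undertake a semi structured interview during the 12 week follow up visit". The number is not a hard limit: the same section says that "further interviews may be required if new data is still presenting itself after the final interview", and that "sampling will continue until eligible participant pool has been exhausted or interviews are not yielding new information". Section 10 repeats that data collection ends at saturation. No variable for choosing interviewees is named, and no reason is given for 8-10.

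**The concern.** Convenience sampling is usually accepted because willing people are hard to find or no list of them exists. Neither applies here: the protocol excludes the unwilling and so creates a full list of people who have agreed, then takes whoever is convenient.

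The stopping rule adds to this. It has two alternative ends, and the second is met once the people interviewed so far stop adding anything. If they resemble each other, that can happen early, and the apparent saturation then reflects their similarity rather than complete coverage.

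What is at stake is the participant part of the secondary objectives, namely acceptability and perception of the intervention. The cohort mixes ischaemic stroke, TIA and peripheral vascular referrals (section 8.2). It enters through emergency admission, inpatient stay or clinic (section 9) and is open to people of any social background (section 3). One stated interview topic is future research on reducing health inequalities. Difficulties met by the least available participants bear directly on that topic and are the most exposed to convenience selection.

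**Working it through.** **Inputs.** Cohort N = 20 (section 8.1). Interviewees n = about 8-10 (section 9). Recruitment of 5 per month for 4 months, within a stated window of 4 to 8 months (section 9.1). Withdrawals are not replaced (section 9.4). The size k of a small group is not given anywhere in the protocol; k = 3 to 6 is an assumption.

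**The plan's own figures.** 5 × 4 = 20 reproduces the target. No calculation is stated for 8-10, so there is nothing to reproduce. It is 8/20 = 40% to 10/20 = 50% of the cohort, leaving 10-12 people without an interview if none are added.

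**Timing.** Interviews fall at week 12, so people become available in enrolment order. At 5 per month, the first 8-10 enrolled come from the first 8/5 = 1.6 to 10/5 = 2.0 months of recruitment. At the slower pace of 20/8 = 2.5 per month, they come from the first 3.2 to 4.0 months. This shows who is available first, not who will be chosen.

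**Benchmark: random selection.** The probability that none of a group of k is among n interviewees is C(20−k, n) / C(20, n).

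For k = 3 this equals (20−n)(19−n)(18−n) / (20 × 19 × 18), with denominator 6,840:

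- n = 8: 12 × 11 × 10 / 6,840 = 1,320 / 6,840 = 19.3%
- n = 9: 11 × 10 × 9 / 6,840 = 990 / 6,840 = 14.5%
- n = 10: 10 × 9 × 8 / 6,840 = 720 / 6,840 = 10.5%

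Over the range of assumed group sizes:

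| Group size k (assumed) | n = 8 | n = 9 | n = 10 |
|---|---|---|---|
| 3 | 19.3% | 14.5% | 10.5% |
| 4 | 10.2% | 6.8% | 4.3% |
| 5 | 5.1% | 3.0% | 1.6% |
| 6 | 2.4% | 1.2% | 0.5% |

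**If interviews are extended.** With k = 3 and n = 12, the figure is 8 × 7 × 6 / 6,840 = 336 / 6,840 = 4.9%. If all 20 are interviewed it is zero.

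**If the pool shrinks.** At the 25% drop-out named in the green column of section 12.1, 15 remain. If all 3 of the group are among them, the chance of missing the group is C(12, 8) / C(15, 8) = 495 / 6,435 = 7.7% with 8 interviews, and C(12, 10) / C(15, 10) = 66 / 3,003 = 2.2% with 10.

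**What this does and does not measure.** These figures show the risk from interviewing fewer than everyone without deliberate coverage. Convenience selection has no known selection probabilities, so no figure can be attached to it. It would be worse than the benchmark if the group is harder to reach than the rest.

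**The case against.** The strongest case for the plan as written has four parts.

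- **More interviews are allowed.** The rule can extend sampling to the whole cohort. This stands as mitigation. It does not settle the matter, because the two ends of the rule are joined by *or*: sampling may stop at perceived saturation whatever groups remain unheard.
- **Access is reasonably good.** Interviews are tied to a visit that every retained participant is due to have, a video option exists (section 10), and interpretation is offered for intervention visits (section 9.3). A reader might infer that those interviewed will in fact be the earliest and easiest to reach. The protocol does not support that as a statement of fact, since it fixes no order of selection. It is a risk.
- **Interviews are not the only source.** The objectives table in section 4 also assigns CRF B and questionnaires to the secondary objectives. Adviser interviews and reflective diaries add further material, so people who are not interviewed are not wholly unheard. This stands and limits the consequence.
- **No comparison is promised.** A reader might infer that the study sets out to contrast experience by diagnosis or deprivation and will fail to do so. Neither contrast is an objective: social background is to be described only. The concern is therefore breadth of coverage and the basis for a saturation claim, not a failed comparison.

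It is also fair to say that the benchmark falls quickly with group size, and that nothing in the protocol suggests that any particular diagnosis will supply only three people.

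**Conclusion.** The point holds as a weakness in how interviewees are selected. The protocol creates a complete frame of people who have agreed to be interviewed and then does not use it. Combined with rolling week-12 interviews and a stop when nothing new is heard, this may favour early or easily reached participants and may let saturation be declared with a diagnosis, setting or social group unheard.

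The size can only be bracketed. Under random selection of 8 to 10, a group of 3 is missed entirely 10.5% to 19.3% of the time and a group of 6 at most 2.4% of the time. This rests on assumed group sizes, no withdrawals and no added interviews. It should not be read as the effect of convenience selection, nor as evidence that purposive selection is needed to rescue the study. The change is a low-cost improvement in a descriptive pilot of 20 people.

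**What to change.** In section 9 (Process Evaluation), replace convenience sampling with purposive maximum-variation selection from the consented cohort:

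- **Variables.** Use a few that are already recorded: diagnosis, recruitment setting, one social-background item from CRF A, and visit mode from the home visit form. The protocol names no deprivation index, so the social item should be chosen from what the form holds.
- **Targets.** Start at about 8-10 interviews and aim for at least one or two interviewees per category, where available. Fixed quotas would not work: diagnoses may overlap, recruitment is not stratified, and the cohort's social spread is unknown while interviews are still rolling.
- **Stopping.** Apply the stop for lack of new information only once the available categories have been covered, and word section 10 to match.
- **Reporting.** Describe the interviewees against the full cohort on the same variables.

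The cost is a change of wording, a short selection grid, modest extra scheduling, and possibly one or two more interviews, which the protocol already permits. The change does not reach people who drop out before week 12; that limit should be stated in the report.

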9.1. Recruitment

20 participants will be recruited over a 4-to-8-month period. The aim is to recruit a conservative 5 participants per month for a total of 4 months to reach a target recruitment of 20 participants. The following routes of recruitment will be used: Potential participants will be identified locally at sites across Aneurin Bevan University Health Board by cardiovascular disease, peripheral artery, and stroke specialists. Including emergency admission, in patient setting or consultant and nurse lead clinics.

9.2. Screening and Eligibility Assessment

Initial identification and eligibility of participants will be confirmed by the clinical team and supported by delegated ABUHB research delivery team.

Potential participants will obtain a Participant Information Sheet (PIS) (via various routes including in hospital setting, at a clinical appointment or posted out with the potential participants outpatient appointment letter.

Electronic screening logs will be kept and will include reason for non-participation. The reason for non-participation will be sought via the ABUHB research delivery team.

